13.2.2 Severity Assessment

Severity Assessment – A qualitative assessment of the degree of intensity of an adverse event as determined by the Investigator or reported to him/her by the subject. The assessment of severity is made irrespective of test article, study treatment or study procedure relationship or seriousness of the event and should be evaluated according to the following scale:

- Mild – Event is noticeable to the subject, but is easily tolerated and does not interfere with the subject's daily activities
- Moderate – Event is bothersome, possible requiring additional therapy, and may interfere with the subject's daily activities
- Severe – Event is intolerable, necessitates additional therapy or alteration of therapy and interferes with the subject's daily activities

13.3. Documentation and Follow-Up of Adverse Events

The recording and documenting of adverse events (ocular and non-ocular) begins when the subjects are exposed to the test article, study treatment or study procedure. Adverse events reported before the use of test article, start of study treatment, or study procedures will be recorded as medical history. However, if the condition deteriorates at any time during the study it will be recorded and reported as an AE. Untoward medical events reported after the subject's exit from the study will be recorded as adverse events at the discretion of the Investigator.

Upon finding an adverse event, the Principal Investigator will document the condition in the subject record and in the eCRFs. He/she will complete the Adverse Event /eCRF.

Complete descriptions of all adverse events must be available in the subject record. All Adverse Events including local and systemic reactions not meeting the criteria for "serious adverse events" shall be captured on the appropriate case report form or electronic data system. All adverse events occurring while the subject is enrolled in the study must be documented appropriately regardless of relationship.

It is the Investigator's responsibility to maintain documentation of each reported adverse event. All adverse events will be followed in accordance with applicable licensing requirements. Such documentation will include the following:

- Adverse event (diagnosis not symptom)
- Drawings or photographs (where appropriate) that detail the finding (e.g., size, location, and depth, etc.)
- Date the clinical site was notified
- Date and time of onset
- Date and time of resolution

- Adverse event classification, severity, and relationship to test articles, as applicable
- Treatment regimen instituted, including concomitant medications prescribed, in accordance with applicable licensing requirements
- Any referral to another health care provider if needed
- Outcome, ocular damage (if any)
- Likely etiology
- Best corrected visual acuity at the discovery of the event and upon conclusion of the event

In addition, if an infiltrate(s) is present, he/she will complete the Corneal Infiltrate Assessment /eCRF. Where necessary, a culture of the corneal lesion will be collected to determine if the infection is microbial in nature. If cultures are collected, the date of culture collection and laboratory utilized will be recorded.

Changes in the severity of an AE shall be documented to allow an assessment of the duration of the event at each level of intensity to be performed. Adverse events characterized as intermittent require documentation of the onset and duration of each episode. Changes in the assessment of relationship to the test article shall also be clearly documented.

Subjects who present with an adverse event shall be followed by the Investigator, within licensure, until all signs and symptoms have returned to pre-treatment status, stabilized, or been satisfactorily resolved. If further treatment beyond licensure is required, the patient will be referred to the appropriate health care provider. The Investigator will use his/her clinical judgment as to whether a subject reporting with an adverse event will continue in the study. If a subject is discontinued from the study, it will be the responsibility of the Investigator to record the reason for discontinuation. The Investigator will also document the adverse event appropriately and complete the Adverse Event eCRF. Any subjects with ongoing adverse events related to the test article, study treatment or study procedures, as of the final study visit date, should be followed to resolution of the adverse event or until referral to an appropriate health care provider, as recommended by the Investigator. Non-ocular adverse events that are not related to the test article, study treatment, or study procedures may be recorded as “ongoing” without further follow-up.

13.4. Reporting Adverse Events

The Investigator will notify the Sponsor of an adverse event by e-mail, facsimile, or telephone as soon as possible and no later than 24 hours from discovery for any serious /significant adverse events, and 2 days from discovery for any non-significant adverse event. In addition, a written report will be submitted by the Principal Investigator to the IEC/IRB according to their requirements (Section 13.4.2). The report will comment whether the adverse event was considered to be related to the test article, study treatment or study procedures.

13.4.1 Reporting Adverse Events to Sponsor

Serious/Significant Adverse Events

The Investigator will inform the sponsor of all serious/significant adverse events occurring during the study period as soon as possible by e-mail, fax, or telephone, but no later than 24

hours following discovery of the event. The Investigator is obligated to pursue and obtain information requested by the Sponsor in addition to that information reported on the eCRF. All subjects experiencing a serious/significant adverse event must be followed up and all outcomes must be reported.

When medically necessary, the Investigator may break the randomization code to determine the identity of the treatment that the subject received. The Sponsor and study monitor should be notified prior to unmasking the test articles.

In the event of a serious/significant adverse event, the Investigator must:

- Notify the Sponsor immediately
- Obtain and maintain in the subject's records all pertinent medical information and medical judgment for colleagues who assisted in the treatment and follow-up of the subject
- Provide the Sponsor with a complete case history which includes a statement as to whether the event was or was not related to the use of the test article
- Notify the IEC/IRB as required by the IEC/IRB reporting procedure according to national regulations

Unanticipated (Serious) Adverse Device Effect (UADE)

In the event of an Unanticipated (Serious) Adverse Device Effect (UADE), the Investigator will submit a report of the UADE to the Sponsor and IEC/IRB as soon as possible, but no later than 24 hours after the Investigator first learns of the effect. This report is in addition to the immediate notification mentioned above.

The Sponsor must conduct an evaluation of the UADE and must report the results of the evaluation to FDA, the IEC/IRB and participating Investigators within 10 working days after the Sponsor first receives notification of the effect.

Non-Serious Adverse Events

All non-serious adverse events, including non-serious adverse device effects, will be reported to the sponsor by the Investigator no later than 2 days from discovery.

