2.5.	Follow-Up Questionnaire	Subjects will respond to the following questionnaires: 1. CLUE Follow-up 2. GSI Product Performance	
2.6.	Visual Acuity	Record the distance Snellen visual acuity with the contact lenses (OD, OS, and OU) to the nearest letter. Subjects must read the smallest line until at least 50% of the letters are read incorrectly.	
2.7.	Quick Contrast Sensitivity	████████ only. Perform the 4 m contrast sensitivity test once OD and OS using the 25-item methodology while wearing the study lenses.	
2.8.	logMAR (ETDRS) Visual Acuity	Perform 4 m distance ETDRS LogMAR visual acuity test OD and OS under the following conditions: 1. Bright room illumination / low contrast charts a. Room illumination >400 lux b. Chart luminance 120-200 cd/m ² c. One low contrast chart per eye. 1) OD: chart LC-1 2) OS: chart LC-2 2. Low room illumination / high contrast charts a. Room illumination <2.5 lux b. Chart luminance 2.0-5.0 cd/m ² c. One high contrast chart per eye. 1) OD: chart HC-1 2) OS: chart HC-2	████████ ████████
2.9.	Subjective Lens Fit Assessment	Subjective Assessment of the Lens Fit. If the fit is graded as unacceptable based on the criteria below, then the subject is discontinued from the study and will not be replaced. 1. Limbal exposure in any gaze 2. Edge lift 3. Insufficient and/or excessive movement in all three movement categories	

Visit 2: Treatment 1 Follow-Up			
Step	Procedure	Details	
2.10.	Surface Deposits	Record any front and back surface lens deposits.	
2.11.	Lens Removal & Storage	Both lenses will be removed and stored wet in a labeled container with Opti-Free® PureMoist®. The lenses can be stored refrigerated or frozen prior to shipment back to the Sponsor. Lenses will be stored at JJVC for 45 days after LSLV for laboratory testing (Section 7.4).	
2.12.	Slit Lamp Findings	
Slit Lamp Classification Scale [REDACTED] will be used to grade the findings. Record only whole numbers. Limbal and Bulbar Conjunctival Hyperemia findings [REDACTED] [REDACTED] and Corneal Staining Assessment [REDACTED] [REDACTED] will be emphasized using a more detailed scale.
 
Note: Findings must be grade 2 or less as graded on the FDA scale [REDACTED] to continue onto Trial Period 2. If the subject is not eligible, they must be followed as an adverse event. Once resolved, the subject is terminated from the study. Adverse events must be reported to the JJVC monitors immediately.
	[REDACTED] [REDACTED] [REDACTED]

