- Central Corneal Opacity
- Central Corneal Neovascularization
- Uveitis
- Endophthalmitis
- Hypopyon
- Hyphemia
- Penetration of Bowman's Membrane
- Persistent Epithelial Defect
- Limbal cell Damage leading to Conjunctivalization

Significant Adverse Events – Those events that are usually symptomatic and warrant discontinuation (temporary or permanent) of the test article (excluding Serious Adverse Events).

Diagnoses and conditions that are considered Ocular Significant Adverse Events include, but not limited to the following:

- Contact Lens Induced Peripheral Ulcer (CLPU)
- Significant Infiltrative Events (SIE)
- Superior Epithelial Arcuate Lesions (SEALS)
- Any Temporary Loss of >2 Lines of BSCVA
- Other Grade 3 or higher corneal findings, such as abrasions or edema
- Non-contact lens related corneal events - e.g. Epidemic Keratoconjunctivitis (EKC)
- Asymptomatic Corneal Scar
- Any corneal event which necessitates temporary lens discontinuation >2 weeks

Non-Significant Adverse Events – Those conditions that are usually asymptomatic and usually do not warrant discontinuation (temporary or permanent) of the test article. However, the Investigator may choose to treat as a precautionary measure.

Diagnoses and conditions that are considered Ocular Non-Significant Adverse Events include, but not limited to the following:

- Non-significant Infiltrative Event (NSIE)
- Contact Lens Papillary Conjunctivitis (CLPC)
- Superficial Punctate Keratitis (SPK)
- Conjunctivitis: Bacterial, Viral, Allergic
- Blepharitis
- Meibomianitis
- Contact Dermatitis
- Localized Allergic Reactions

- Any corneal event not explicitly defined as serious or significant adverse event, which necessitates temporary lens discontinuation < 2 weeks

Adverse Device Effect (ADE) – An ADE is an “adverse event related to the use of an investigational medical device.

Note 1 to entry: This definition includes adverse events resulting from insufficient or inadequate instructions for use, deployment, implantation, installation, or operation, or any malfunction of the investigational medical device.

Note 2 to entry: This definition includes any event resulting from use error or from intentional misuse of the investigational medical device.”¹

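### The closing rule of Protocol 13.4.1 gives all non-serious adverse events 2 days, which takes in the significant events that 13.4 and the start of 13.4.1 put on a 24-hour limit

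*Protocol*

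**What the plan says.** Protocol 13.1 sorts adverse events into three classes: serious, significant and non-significant. The significant class is defined as "Those events that are usually symptomatic and warrant discontinuation (temporary or permanent) of the test article (excluding Serious Adverse Events"), followed by a non-exhaustive list of ocular examples.

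Protocol 13.4 then sets the time limits for telling the sponsor: "no later than 24 hours from discovery for any serious /significant adverse events, and 2 days from discovery for any non-significant adverse event". The dividing line there runs between significant and non-significant.

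Protocol 13.4.1 opens under a serious/significant heading: "The Investigator will inform the sponsor of all serious/significant adverse events occurring during the study period as soon as possible", with the same 24-hour limit. It adds that the sponsor is to be notified immediately of such an event.

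The section closes under a separate heading, for events that are not serious, with this rule: "All non-serious adverse events, including non-serious adverse device effects, will be reported to the sponsor by the Investigator no later than 2 days", counted from the time of discovery. Here the dividing line runs between serious and non-serious, and significant events are not excepted.

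The SAP sets no reporting limit. Its section 12.1 provides only for listings of adverse events and serious adverse events.

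**The concern.** The two dividing lines do not coincide. Between them lies the whole significant class, which is non-serious by definition but grouped with serious events for reporting. These are the most important events short of serious ones in a lens study. Section 1 also says that lenses from the new manufacturing line are being evaluated clinically for the first time.

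Two things are at stake. A site that looks up only the non-serious paragraph could report a significant corneal event later than 13.4 allows. A monitor would also find it hard to say whether that report is a protocol deviation, because one paragraph permits it and two others do not.

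**Working it through.** No figure in the plan needs reproducing. The check sets the classes of 13.1 against each stated limit.

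**Step 1: is a significant event always non-serious?** Yes. The 13.1 definition excludes serious events, so the significant class lies wholly within the non-serious group.

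**Step 2: limit for each class, read literally.**

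| Class (13.1) | 13.4 | 13.4.1, serious/significant part | 13.4.1, closing non-serious part |
|---|---|---|---|
| Serious | 24 hours | 24 hours | not covered |
| Significant (non-serious) | 24 hours | 24 hours | 2 days |
| Non-significant | 2 days | not covered | 2 days |

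Only the middle row carries two different limits.

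**Step 3: which events are in that row?** Section 13.1 lists eight conditions as examples. They include peripheral ulcers, significant infiltrative events, superior epithelial arcuate lesions and "Other Grade 3 or higher corneal findings, such as abrasions or edema". All eight are under both limits.

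**Step 4: size of the gap.** 2 days = 48 hours, and 48 − 24 = 24 hours.

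**Step 5: can both limits be met?** Yes. A report at or before 24 hours is also before 48 hours, so the shorter limit sits inside the longer one. The two rules give different answers only for a report made between 24 and 48 hours. A significant event reported at 36 hours, for example, meets the closing paragraph of 13.4.1 but breaches 13.4 and the first part of 13.4.1.

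**Step 6: does changing one phrase cure it?** No. The closing sentence names non-serious adverse events and also, separately, non-serious adverse device effects. A lens-related peripheral ulcer is a significant, non-serious device effect. If only the first phrase changed, the second would still place that ulcer on the 2-day limit.

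**The case against.** The strongest reply is that the protocol, read as a whole, leaves little doubt. Significant events are named under the 24-hour limit in 13.4, named again under their own heading in 13.4.1, and made subject there to immediate notification. Against these specific statements, the closing paragraph looks like a slip of label. This reply largely stands. It limits the consequence but does not remove the contradiction, because the closing paragraph is a separately headed rule with no exception.

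It also rules out several stronger readings that a reader might infer:

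- **That the permitted delay doubles from 24 to 48 hours.** The documents do not support this. With nested limits, a site following all the text is still bound by 24 hours.
- **That the slit lamp notes add a conflicting third limit.** Steps 2.12, 3.13 and 4.12 concern findings above Grade 2 and say "Adverse events must be reported to the JJVC monitors immediately". That agrees with the immediate notification in 13.4.1. It also means that a Grade 3 or higher finding at a scheduled follow-up already falls under an instruction to report at once, which narrows the exposure.
- **That stopping under section 11 is compromised.** The events named there as possible grounds for halting dispensing are unanticipated serious device effects and serious events whose relationship cannot be ruled out. The disputed paragraph touches neither. Section 11 does have the sponsor evaluate all adverse events, but its call for speed concerns termination once an unreasonable risk has been determined. It is not a reporting limit.
- **That the two-week criterion puts events on the slower limit.** One significant example is "Any corneal event which necessitates temporary lens discontinuation >2 weeks", and the matching non-significant item uses less than 2 weeks, so exactly 2 weeks falls under neither. The criterion can be read as a judgement of expected need made when the event is found. It is also one item in an open list, and no practical effect is shown. It is at most a minor drafting note.

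**Conclusion.** The point holds as an internal inconsistency in an operative safety-reporting rule. The significant class, and only that class, falls under two stated limits 24 hours apart. The practical risk is limited to a site that relies on the closing paragraph of 13.4.1 alone, and to uncertainty over how a report made between 24 and 48 hours should be classed.

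This rests on reading the class definitions in 13.1 and the closing paragraph literally. How often a site would in fact rely on that paragraph cannot be estimated from the documents. No endpoint, analysis population, power or type I error is affected. The correction is worth making because it is cheap and concerns safety reporting, not because harm has been shown.

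**What to change.** Reconcile the closing paragraph of Protocol 13.4.1 with the split in 13.4. The change that follows the protocol's own wording has three parts:

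1. Change the paragraph heading from non-serious to non-significant adverse events.
2. Make the same change to the first phrase of the sentence, on adverse events.
3. Make it also to the second phrase, on adverse device effects, for the reason in step 6 of the check.

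Leave the instruction to report immediately in steps 2.12, 3.13 and 4.12 unrelaxed. Those notes should not be rewritten to a 24-hour limit for the sake of uniformity.

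Optionally, in the same edit, make the two duration items in 13.1 meet so that exactly 2 weeks belongs to one class.

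The cost is a few words in the protocol and a line in site training. No new limit is introduced, no SAP text changes and no analysis is affected.

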13.4.2 Reporting Adverse Events to the Responsible IEC/IRB and Health Authorities

Adverse events that meet the IEC/IRB requirements for reporting must be reported within the IEC/IRB's written guidelines. Each clinical site will refer to and follow any guidelines set forth by their Approving IEC/IRB. Each clinical site will refer to and follow any guidelines set forth by their local governing Health Authorities.

The Sponsor will report applicable Adverse Events to the local health authorities according the written guidelines, including reporting timelines.

13.4.3 Event of Special Interest

None.

13.5. Reporting of Pregnancy

Subjects reporting pregnancy (by self-report) during the study will be discontinued after the event is recorded as an Adverse Event. Once discontinued, pregnant participants and their fetuses will not be monitored for study related purposes. At the Investigator's discretion, the study participant may be followed by the Investigator through delivery. However, this data will not be collected as part of the clinical study database. Pregnant participants are not discontinued from contact lens or solution related studies for safety concerns, but due to general concerns relating to pregnancy and contact lens use. Specifically, pregnant women are discontinued due to fluctuations in refractive error and/or visual acuity that occur secondary to systemic hormonal changes, and not due to unforeseen health risks to the mother or fetus.

14. STATISTICAL METHODS

This section is a general outline of the statistical methods that will be implemented in this clinical trial. More details will be included in the stand-alone Statistical Analysis Plan (SAP). The SAP will be developed and finalized prior to database lock.

14.1. General Considerations

Statistical Analysis will be undertaken by the sponsor or under the authority of the sponsor. A general description of the statistical methods to be implemented in this clinical trial is outlined below.

All data summaries and statistical analyses will be performed using the SAS software Version 9.4 or higher (SAS Institute, Cary, NC). Throughout the analysis of data, the results for each subject/eye will be used when available for summarization and statistical analysis. Unscheduled visits will be summarized separately and will be excluded from the statistical analysis.

Summary tables (descriptive statistics and/or frequency tables) will be provided for all baseline variables, efficacy variables and safety variables as appropriate. Continuous variables will be summarized with descriptive statistics (n, mean, standard deviation [SD], median, minimum and maximum). Frequency count and percentage of subjects or eyes within each category will be provided for categorical data.

14.2. Sample Size Justification

This study was designed and powered to show non-inferiority of the Test lens compared to the Control lens with respect to logMAR Visual Acuity, Slit Lamp Findings (Grade 3 or higher), CLUE comfort, handling and overall quality of vision. It was assumed there was no difference between the Test and Control lens with respect to visual acuity and slit lamp findings. Based on data from 3 historical studies, it was assumed there was a 5-, 3- and 4-point difference between the Test and Control lenses with respect to CLUE comfort, handling and overall quality of vision, respectively.

In addition to the endpoints mentioned above this study was also powered to demonstrate non-inferiority of the Test lens relative to the Control lens with respect to vision satisfaction in

bright lighting, overall quality of vision indoors and the proportion of eyes with acceptable fitting while the Test lens is significantly superior to 90%.

Unless otherwise specified, the sample size was calculated to achieve a minimum statistical power of 80% and a type I error of 5%.

A total of 5 historical studies were utilized in the sample size calculation. Table 4 displays the studies, their corresponding study design and the number of subjects enrolled and completed per-protocol.

Table 4: Historical Studies Included in Sample Size Calculation

Study	Study Design	Endpoints Collected	No. Enrolled	No. Completed Per-Protocol
██████████	2X3 Crossover	CLUE, SLF Lens Fit	135	132
██████████	2X3 Crossover	CLUE, Visual Acuity (logMAR), SLF, Lens Fit	133	121
██████████	2X3 Crossover	CLUE, SLF Lens Fit	92	78
██████████	Single-Arm	SLF, Lens Fit	54	48
██████████	Single-Arm	SLF, Lens Fit	56	41

Table 5: Descriptive Summary of CLUE Scores by Domain Pooled Across Historical Studies
– 2-Week Follow-up Evaluation

CLUE Domain [Mean(SD) ¹]	Test	Control
Comfort	66.46 (22.20)	61.19 (24.20)
Handling	69.61 (19.18)	66.79 (20.01)
Overall Quality of Vision	64.15 (18.83)	60.33 (22.29)

¹SD = Standard Deviation

Table 6: Descriptive Summary of Visual Acuity (logMAR) - █ – 2-Week Follow-up Evaluation

Visual Acuity High Illumination High Contrast	Test	Control
[Mean(SD) ¹]	-0.0928 (0.08253)	-0.0726 (0.08011)

¹SD = Standard Deviation

Table 7: Descriptive Summary of Mechanical Lens Fitting Pooled Across all Historical Studies

Any Unacceptable Lens Fit¹ [n(%)]	Test n (%)	Control n (%)
Fitting Evaluation	0 (0.0)	0 (0.0)
2-Week Follow-up	0 (0.0)	0 (0.0)

¹The percent of any unacceptable fit is calculated using Total Unique eyes as a denominator

Table 8: Descriptive Summary of Slit Lamp Findings Pooled Across all Historical Studies

SLF Grade 2	Test n (%)	Control n (%)
Corneal Edema	0 (0.0)	0 (0.0)
Conjunctival Injection	59 (6.86)	59 (21.85)
Tarsal Abnormalities	51 (5.93)	24 (8.89)
Corneal Neovascularization	3 (0.35)	0 (0.0)
Corneal Staining	3 (0.35)	0 (0.0)
Other Findings	0 (0.0)	0 (0.0)
Total Eyes (N)	860	270
<hr/>		
Any SLF Grade 2 ²	116 (13.48)	83 (33.74)
Any SLF Grade 3+	0 (0.0)	0 (0.0)
Total Unique Eyes	860	270
Total Unique Subjects	430	135

%= nx100/N; SD=Standard Deviation

¹All SLF reported for this study are combined for the purposes of summarizing

² The percent (%) of Any Grade 2 is calculated using the Total Unique Eyes as the denominator

Table 9: Descriptive Summary of Individual Items from [REDACTED] – 2-Week Follow-up

Questionnaire Item/ Response	Test	Control
Vision Satisfaction in Bright Light [n(%)]		
Strongly Agree	72 (29.75)	51 (21.07)
Agree	129 (53.31)	130 (53.72)
Neither Agree Nor Disagree	24 (9.92)	21 (8.68)
Disagree	17 (7.02)	33 (13.64)
Strongly Disagree	0 (0.0)	7 (2.89)
Overall Quality of Vision Indoors [n (%)]		
Excellent	100 (55.25)	80 (43.96)
Very Good	55 (30.39)	62 (34.07)
Good	23 (12.71)	30 (16.48)
Fair	3 (1.66)	7 (3.85)
Poor	0 (0.0)	3 (1.65)

CLUE Comfort

Sample size calculation for CLUE comfort was carried out using an approximation of the power of an F-test derived from the non-centrality parameter calculated from the observed F statistic of a linear model¹².

Model details:

CLUE comfort was analyzed using a linear mixed model. Lens type was included as the only fixed effect. An unstructured (UN) covariance matrix was used to model the correlation between measurements on the same subject across study periods. Below is the variance-covariance matrix used in the CLUE Comfort model.

$$\sum_{comfort} \begin{pmatrix} 397.18 & 142.48 & 144.55 \\ 142.48 & 411.89 & 210.90 \\ 144.55 & 210.90 & 370.83 \end{pmatrix}$$

Visual Performance (logMAR)

Sample size calculation for visual performance (logMAR) was carried out using an approximation of the power of an F-test derived from the non-centrality parameter calculated from the observed F statistic of a linear model¹².

Model details:

visual performance was analyzed using a linear mixed model. Lens type was included as the only fixed effect. A compound symmetric (CS) covariance matrix was used to model the correlation between measurements on the same subject across study periods. Below is the variance-covariance matrix used in the visual performance model.

$$\sum_{\text{visual performance}} \begin{pmatrix} 0.003518 & 0.000374 & 0.000374 \\ 0.000374 & 0.003518 & 0.000374 \\ 0.000374 & 0.000374 & 0.003518 \end{pmatrix}$$

Acceptable Lens Fit

Acceptable lens fit is a binary response as y=1 if a subject eye has an acceptable fit and 0 otherwise. Indicated by the historical data there were no observed unacceptable lens fittings for either the Test or Control lens therefore, the common reference rate of 95% was selected for the sample size calculation, since this is considered to be a more conservative reference proportion. Assuming a correlation 0.80 between measurements within the same subject and period; and assuming a correlation of 0.50 between measurements within the same subject across periods. A total of 2000 replicating trials were simulated to estimate a sample size with a minimum statistical power of 80%.

Slit Lamp Findings

There were no Grade 3 or higher SLFs observed in any of the historical studies. Assuming no difference between study lenses and a correlation 0.80 between left and right eyes within the same subject and period; and a correlation of 0.50 between measurements within the same subject across periods (intra-subject correlation). A reference rate of no more than 10% was assumed (worse-case scenario) with a non-inferiority odds ratio margin of 2. A total of 2000 replicating trials were simulated, each replicated sample was analyzed using a generalized estimating equation (GEE) model with a binary distribution and the logit as the link function. Each model included lens type as the only fixed, eye was included as a random effect. The Odds ratio and corresponding 95% confidence interval was used estimate differences between the Test and Control lenses. The upper limit of each 95% confidence interval was compared to 2; if the upper limit was below 2 then NI=1; otherwise NI=0. Statistical power was calculated at the average NI. A sample size of 50 was chosen to achieve a minimum statistical power of 80%.

The non-inferiority odds ratio margin of 2 corresponds to no more than a 5% difference between the Test and Control lenses assuming the Control reference rate does not exceed 10%.

Individual Questionnaire Items

Overall quality of vision outdoors and vision satisfaction in bright lighting sample size estimates were calculated using historical data from [REDACTED]. One-thousand boot strap

samples were simulated based on the historical data. For each replicated sample a generalized linear mixed model was used with a multinomial distribution and the cumulative logit as the link function. Lens wear sequence, lens type, period and first order carryover effect were included in the model as fixed effects. A variance component (VC) covariance structure was used to model the measurements between subjects across study periods.

The non-inferiority cumulative odds ratio margin of 0.67 corresponds to no more than a 10% difference between the Test and Control lenses assuming there is no difference between study lenses.

Table 10: Sample Size Estimates and Power Calculations for Primary Endpoints

Endpoint	Number per Subjects to Complete	Power
Distance Monocular Visual Acuity (logMAR)	4	80%
SLFs (Grade 3 or Higher)	50	80%
Acceptable lens Fit	65	80%
CLUE Comfort	30	87%
Vision Satisfaction in Bright Lighting	48	81%

Table 11: Sample Size Estimates and Power Calculations for Secondary Endpoints

Endpoint	Number per Subjects to Complete	Power
CLUE Handling	30	81%
CLUE Overall Quality of Vision	30	82%
Overall Quality of Vision Indoors	95	81%

As indicated in Table 10 and 11 above, the sample size chosen for this study was primary driven by overall quality of vision indoors. The plan is to enroll 120 eligible subjects with a target of 105 subjects to complete the study. During the enrollment period, the subject dropout rate will be closely monitored, if an unexpectedly high dropout rate is observed, then the targeted total enrollment number may be increased accordingly to ensure that a minimum of 105 subjects complete the study.

